#### 7.4 Risk/Benefit Assessment

The probable benefits of the software are based on the data that will be collected in the clinical study being conducted to support PMA supplement approval.

The software has no significant risk of direct harm to the patient.

### 8. Reader Selection and Training

#### 8.1. Purpose

The purpose of the training process is to ensure that each reader selected for the reading session has been adequately trained to evaluate the DBT image sets on the ASPIRE Bellus II workstation.

#### 8.2. Selection and Qualification Criteria for Readers

This study will be conducted with radiologists of varying experience levels, from both community and academic practices. These radiologists were not associated with the acquisition or original clinical review of cases.

Base qualification criteria: All readers must meet the following base criteria:

- Are board-certified
- Are MQSA-qualified for DBT interpretation

### 8.3. Conduct of the Training Process

Training will include review of the case report forms to ensure reader understanding of the mammographic features they will be evaluating images based on, as well as the 5-point scale they will be utilizing to grade each image set. Readers will be specifically instructed to use the score=0 sparingly. GCP will also be reviewed and documented via attestation form during the training process.

Training will also consist of a hands-on session at the workstation to provide the readers with an overview of its pertinent DBT-specific functionality.

Following the successful completion of the reader training, the readers will independently review and score each of the approximately 100 image sets at their own designated workstation. Interpretation of mammography images will be performed in a controlled environment with consistent lighting. The review workstations will be preloaded with the cases. The reading time allowed per image set will not be limited. A lunch break will be offered during the reading session, and radiologists will be encouraged to take a 5-10 minute break each hour, as needed. Each reader will dictate their evaluations to a trained scribe, who will enter the dictation onto a paper CRF. Each reader will sign an attestation form verifying the documented information.

#### 8.4 Conduct of the Reading Process

### 8.4.1 Purpose and Conduct

The purpose of the reading process is for the readers to evaluate, side-by-side, images of the same breast reconstructed with the modified and original processing methods.

Readers will compare several general mammographic features. Readers will be asked to grade each feature on each view (CC and MLO) using the following 5-point scale:

- -2 (left image much superior)
- -1 (left image somewhat superior)
- 0 (left and right images are equivalent)
- +1 (right image somewhat superior)
- +2 (right image much superior)

The list of individual general features and three lesion-specific features is given in Table 3. Note that the results of the three lesion-specific features as well as diagnostic confidence (#8-11 below) will not be evaluated as part of this study. Readers will be specifically instructed to use the score=0 sparingly.

Table 3. Mammographic Features to be Graded

- 1. Exposure, assessing visualization of the adipose and fibroglandular tissues and visualization of breast tissue underlying the pectoralis muscle, separately;
- 2. Breast compression, assessing overlapping breast structures, uniformity of exposure of fibroglandular tissues, adequacy of penetration of thicker portions of the breast, exposure of thinner areas, and motion unsharpness;
- 3. Image contrast for differentiation of subtle tissue density differences; permitting image contrast assessment adjustment of the window and level settings.
- 4. Sharpness, assessing the edges of fine linear structures, tissue borders, and benign calcifications;
- 5. Tissue visibility at the skin line;
- 6. Noise, i.e., noise obscuring breast structures or suggestive of structures not actually present;
- 7. Artifacts due to image processing, detector failure and other factors external to the breast on soft-copy displays; and
- 8. Ability to characterize a Mass (When Present) based on conspicuity, margin sharpness, shape;
- 9. Ability to characterize Calcifications (When Present) based on conspicuity, sharpness/shape, distribution;
- 10. Ability to characterize an Architectural Distortion (When Present) based on conspicuity, sharpness;
- 11. Diagnostic confidence.

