Evaluable Subject	Based on acquisition-site data, an evaluable subject is a subject with known true clinical status and with complete DBT and FFDM examinations (four standard views), in which there is sufficient anatomical coverage, sufficient contrast, no significant motion or other artifacts, limited noise, and similar positioning.
FMSU2013-004A	Acquisition of Digital Mammography and Breast Tomosynthesis Images for Clinical Evaluation of Fujifilm Digital Breast Tomosynthesis
FMSU2017-003	A Feature Comparison Study to Evaluate the Modified Processing of Fujifilm's ASPIRE Cristalle with Digital Breast Tomosynthesis Option as Compared to the Original Processing
Fujifilm	FUJIFILM Medical Systems, U.S.A., Inc.
IA Site DBT Reader	An image-acquisition site reader is an MQSA-qualified radiologist who interprets the DBT images at the time of image acquisition (see FMSU2013-004A).
Image Set	One (1) image with Original Processing, and one (1) image with Modified Processing of two views (CC and MLO) of the same breast.
Modified Processing	Fujifilm's ASPIRE Cristalle with Digital Breast Tomosynthesis Option with a) iterative super-resolution reconstruction (ISR) and b) Dynamic Visualization II for Mammography (DVIIm = EDR2m + MFP2) presentation processing.
Negative Case	A negative case is defined as a case where there are no abnormal areas or malignant (cancer) findings within a year (within 320 to 455 days) from the original screening examination.
Non-Cancer Case	A biopsy benign case, or a recall case, or a normal case.
Original Processing	Fujifilm's ASPIRE Cristalle with Digital Breast Tomosynthesis Option with FDA-approved filtered back projection (FBP) with EDR and MFP presentation processing.
Prior Mammogram	Historical mammogram acquired on any media – including screen-film, digitized image, FFDM and/or DBT.
Recall Case	A case where there is a suspicious area(s) identified in the screening exam that needs additional work-up to determine if the area is cancerous or not. This is determined at the IA site.
Standard views	Standard CC and MLO views for each breast (RCC, LCC, RMLO, LMLO).

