#### Inclusion Criteria

- Eligible subjects under protocol FMSU2013-004A, defined as female subjects with complete FFDM and DBT examinations, in which there is sufficient anatomical coverage, sufficient contrast, and no significant motion or other artifacts, as determined by the image-acquisition sites.
- Meet none of the exclusion criteria under protocol FMSU2013-004A.

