### 8.4.4 Workflow for the Interpretation of Cases

Readers will be shown side-by-side images of the same breast reconstructed with the modified and original processing methods. One breast per subject (two views per breast) will be assessed by the readers. Readers will be blinded to the image reconstruction and processing methods. Each reader will be given a unique sample of cases to review. The order of the subjects and location (left or right review workstation high resolution monitor) of the images with modified processing will be randomized for each reader.

Within each stratum, cases will be randomly selected so that 10% have extremely dense breasts, 40% have heterogeneously dense breasts, 40% have scattered fibroglandular breasts, and 10% have fatty breasts.

Readers may interpret the preloaded cases in their assigned randomized order with the use of barcode scanner/barcodes.

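### Does telling readers to use score 0 sparingly leave features 2 and 7 to be decided by an unstated convention for features that look alike on both images?

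*Protocol*

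**What the plan says.** The synopsis (study design), section 8.3 and section 8.4.1 each give the instruction; in 8.4.1 it reads "Readers will be specifically instructed to use the score=0 sparingly". The synopsis and 8.4.1 also define the scale, with 0 meaning that the two images are equal on that feature. Section 9 and SAP section 1 count a 0, or any score favouring the modified image, as non-inferior. They test the pooled proportion against 0.50 for each feature and require rejection on all seven.

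Table 3 in section 8.4.1 ends feature 2 with "exposure of thinner areas, and motion unsharpness" and gives feature 7 as "Artifacts due to image processing, detector failure and other factors external to the breast on soft-copy displays". A presence condition appears only for lesion features 8 to 10, for example "Ability to characterize a Mass (When Present) based on conspicuity, margin sharpness, shape", and those features are not evaluated.

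The inclusion criteria in 7.3.2 require "no significant motion or other artifacts, as determined by the image-acquisition sites"; the definition of an evaluable subject has "no significant motion or other artifacts, limited noise, and similar positioning". Section 8.4.4 has readers compare "images of the same breast reconstructed with the modified and original processing methods" and says that the case order and the monitor position of the "images with modified processing will be randomized for each reader".

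**The concern.** Motion blur, detector faults and external artifacts arise when the images are acquired, and both images in a set come from one acquisition. The case screen also removed significant examples. For these items, absent on both or the same on both is an ordinary answer, but the only guidance added to the scale discourages 0. The documents do not say how that guidance applies when nothing differs.

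The two possible responses score very differently. A 0 is a full success. A forced pick, with the side of the modified image randomized, succeeds about half the time. Six readers could settle this in different ways. A feature on which nothing is worse might then fail, and with it the all-seven conclusion. Under free use of 0, a feature might pass mainly because cases were screened to look alike.

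**Working it through.** **The plan's own figures.** Section 9.3 and SAP section 2 use M = {1.96·√0.25 + 0.84·√[p(1−p)]}² / (p−0.5)², divided by six readers.

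| p | M | M/6 | Table 4 |
|---|---|---|---|
| 0.55 | 781.6 | 130.3 | 131 |
| 0.56 | 542.1 | 90.3 | 91 |
| 0.57 | 397.6 | 66.3 | 67 |
| 0.60 | 193.6 | 32.3 | 33 |

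The table reproduces. The pass chance for n independent scores is Φ{[(p−0.5)√n − 0.98] / √[p(1−p)]}. At p = 0.56 and n = 600 this is Φ{(1.470 − 0.98)/0.496} = Φ(0.987) = 83.8%, which agrees with the plan's statement of slightly more than 80%.

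**Sensitivity to zeros.** Suppose a feature is tied in every comparison, a share z is scored 0, and the rest split evenly. Then p = z + (1−z)/2 = 0.5 + z/2. The tie share and the split are assumptions; the documents give neither. Results are shown for 600 scores (two views fully correlated) and 1200 (two views independent).

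| z | p | Pass, 600 | Pass, 1200 |
|---|---|---|---|
| 0% | 0.50 | 2.5% | 2.5% |
| 5% | 0.525 | 23% | 41% |
| 10% | 0.55 | 69% | 93.5% |
| 12% | 0.56 | 84% | 99% |
| 20% | 0.60 | 99.9% | about 100% |

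The sensitivity is real. The first row is simply the type I error stated in section 9.3; it applies to any feature whose true proportion is 0.50.

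**Does an absent item make a tied feature?** Each feature receives one grade per view, so the grade covers everything listed under it.

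- Feature 2 has five elements. Motion blur is one. The others are overlap of structures, evenness of exposure in glandular tissue, penetration of thick regions and exposure of thin regions. New reconstruction and presentation processing can change how these look, so a case without motion is still gradable.
- Feature 7 names image-processing artifacts first. Section 6 expects the new reconstruction to make artifacts less severe, so a difference between the paired images is anticipated. The screen removed only significant artifacts, as judged by the acquisition sites, and does not address artifacts that the new processing adds or removes.

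**What the remaining comparisons do.** Let a be the share of comparisons tied on the whole feature, h the share of those scored 0 (the rest forced, split evenly), and q the non-inferior share among the others. Then p = a[h + (1−h)/2] + (1−a)q. With a = 50% (assumed) and 600 scores:

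| h | q | p | Pass |
|---|---|---|---|
| 0 | 0.50 | 0.25 + 0.25 = 0.50 | 2.5% |
| 0 | 0.62 | 0.25 + 0.31 = 0.56 | 84% |
| 0 | 0.75 | 0.25 + 0.375 = 0.625 | about 100% |
| 0 | 0.25 | 0.25 + 0.125 = 0.375 | about 0% |
| 1 | 0.25 | 0.50 + 0.125 = 0.625 | about 100% |

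Rows two and three show that even if every tie is forced, a preference for the modified image elsewhere can carry the feature. The last row shows what free use of 0 allows: the original is better in 75% of the comparisons that differ, yet the feature passes. Sparing use limits that outcome.

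**The case for a change.** The strongest case for acting is that training pulls readers away from the scale's own definition of 0, and that a forced +1 or −1 cannot later be told from a real preference. Each reader sees different cases, so differences in convention between readers cannot be separated from case mix. Exact equality is not needed for harm: with a = 25%, all forced, and q = 0.56, p = 0.125 + 0.42 = 0.545, and the pass chance at 600 falls from 84% to 60%. One sentence and a tick box for absent or same on both would cost little.

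Part of this stands. Sparing use is not defined, absence on both images is not named for features 1 to 7, and the result responds sharply to the share of zeros.

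The rest does not carry a change. Complete forcing is not what the protocol prescribes, because readers are given a 0 and told what it means. The loss from forcing is mainly a missed pass, borne by the sponsor. An instruction to score 0 whenever a listed item is absent could also do harm: with motion screened out, it could be read as requiring 0 on feature 2 in most cases, making that feature a near-automatic pass even if penetration or exposure were worse. A supportive table of tied comparisons would leave the decision rule as it is. Finally, section 8.3 says training covers the case report forms and the scale; those materials are not among the documents, so further guidance there can be neither confirmed nor excluded.

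**Conclusion.** No change to the plan is needed. There is a small gap in the scoring guidance, and readers and trainers can fill it from the scale as written: 0 is for a feature that, taken as a whole, is equivalent on both images, and sparing use applies otherwise. Discouraging a score that counts as success is a fair trade-off. It risks missing a pass on a truly tied feature, and in return it limits passes built on ties.

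The largest effect, from 2.5% with no zeros to 84% with 12% zeros at 600 scores, requires a feature tied in every comparison and an even split of forced picks. Nothing in the documents supports that for feature 2. For feature 7 ties are more plausible, but section 6 expects a processing difference there. The true tie share is unknown, so how much the convention matters in practice cannot be settled from the documents; no error in the plan has been shown.

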### **Definitions**

	Ţ
ACR® BI-RADS®	a. The breasts are almost entirely fatty
Breast Tissue	b. There are scattered areas of fibroglandular density
Composition	c. The breasts are heterogeneously dense, which may obscure small masses
(Density) Categories	d. The breasts are extremely dense, which lowers the sensitivity of mammography
	Assigned by reader; 0 = Incomplete - Need Additional Imaging Evaluation and/or Prior Mammograms for Comparison
	1 = Negative
	2 = Benign
ACR ® BI-RADS ® Assessment Categories	3 = Probably Benign. Management: Short-interval (6-month) follow-up or continued surveillance mammography
Categories	4 = Suspicious. Management: Tissue diagnosis.
	4A = Low suspicion for malignancy
	4B = Moderate suspicion for malignancy
	4C = High suspicion for malignancy
	5 = Highly Suggestive of Malignancy
ASPIRE Bellus II	Fujifilm mammography viewer (see Appendix A) where the FFDM and DBT images are displayed and reviewed by the physician.
ASPIRE Cristalle with DBT Option	Fujifilm's Mammography Acquisition System (see Appendix A) which generates both FFDM and DBT images.
Benign Case	A case in which all lesions are confirmed as benign by a biopsy or surgery and no other lesions are biopsy-malignant.
Cancer Case	A case in which at least one lesion is confirmed as malignant by biopsy or surgery.
Case	Two views (CC and MLO) of one breast.
	Each DBT Examination has two parts:
DBT Examination	
 
Acquisition: Acquisition of DBT images for each of the standard bilateral CC and MLO views (RCC, LCC, RMLO, LMLO) using the ASPIRE Cristalle.
 
Review: DBT images are displayed and interpreted by the physician on the ASPIRE
 

	Bellus II.
DBT Images	A series of mammograms, which are reconstructed from multiple low-dose projection images captured by the ASPIRE Cristalle with the x-ray tube rotated at a number of small offset angles over a limited angular range while the breast remains compressed and unmoved.
DBT Read	The physician reads (interprets) the DBT images displayed on the ASPIRE Bellus II (see Appendix A)
DBT Views	A series of cross-sectional views of the DBT images for each of the CC and MLO views for each breast.

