# FEATURE COMPARISON STUDY DESIGN

Six MQSA-qualified and board-certified mammographers representing various experience levels, will be shown DBT images of a breast with the modified processing side-by-side the same breast with the original processing. One breast per subject (two views per breast; CC and MLO) will be evaluated by the readers. Readers will be blinded to the image reconstruction and presentation processing methods. Each reader will be given a different sample of cases to review. Approximately 600 total cases (100 cases per reader) will compose the sample. The order of the subjects and location (left or right review workstation high resolution monitor) of the images with modified processing will be randomized for each reader.

Readers will compare several general mammographic features. Readers will be asked to grade each feature on each view (CC and MLO) using the following 5-point scale, with specific training to use the score=0 category sparingly:

- -2 (left image much superior)
- -1 (left image somewhat superior)
- 0 (left and right images are equivalent)
- +1 (right image somewhat superior)
- +2 (right image much superior)

Interpretation instructions: The reader will complete the CRFs for each case for both CC and MLO views. The list of individual general mammographic features and lesion specific features are outlined below. Note that the results of the three lesion-specific features as well as diagnostic confidence (#8-11 below) will not be evaluated as part of this study.

- 1. Exposure, assessing visualization of the adipose and fibroglandular tissues and visualization of breast tissue underlying the pectoralis muscle, separately;
- 2. Breast composition, assessing overlapping breast structures, uniformity of exposure of fibroglandular tissues, adequacy of penetration of thicker portions of the breast, exposure of thinner areas and motion unsharpness;
- Image contrast for differentiation of subtle tissue density differences; permitting image contrast assessment adjustment of the window and level settings;
- 4. Sharpness, assessing the edges of fine linear structures, tissue borders, and benign calcifications;
- 5. Tissue visibility at the skin line;
- 6. Noise, i.e., noise obscuring breast structures or suggestive of structures not actually present:
- 7. Artifacts due to image processing, detector failure and other factors external to the breast on soft-copy displays; and

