### 7.3.3. Case selection and Targeted Distribution

Cases will be randomly selected from Fujifilm's existing library (collected under protocol FMSU2013-004A). A stratified randomization is proposed where the strata and proposed sampling proportions are summarized in Table 2. Within each stratum, cases will be randomly selected so that approximately 10% have extremely dense breasts, 40% have heterogeneously dense breasts, 40% have scattered fibroglandular breasts, and 10% have fatty breasts.

Table 2. Sampling Plan

Stratum, defined by Reference Standard*	# available subjects	Overall sample composition	# cases per reader	Total # cases
Cancer: (N=229)				
Architectural Distortion	21		3-4	21
Microcalcification	86	38%	14-15	86
Asymmetry	19	30%	3-4	19
Mass	95		15-16	95
Other	8		1-2	8
Biopsy Benign: (N=457)				
Architectural Distortion	19		3-4	19
Microcalcification	212	32%	10	60
Asymmetry	43	3270	7-8	43
Mass	158		9	54
Other	25		2-3	15
Recalled/No Biopsy	98	10%	10	60
Negative	234	10%	10	60
Unknown	209	10%	10	60
Total	1227	100%	100	600

\*There are 1031 biopsied lesions in 894 subjects available for selection for this study. Because there are subjects with multiple lesions, cases in the table are organized first by the presence/absence of a malignant lesion, and then by presence/absence of an AD (and possibly another lesion), microcalcification, asymmetry, mass, and other, respectively. There were 208 subjects with lesions but no definitive biopsy diagnosis, including 24 ADs, 24 microcalcifications, 75 asymmetries, and 49 masses.

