### 9. Statistical Analysis

The proportion of cases where the readers judged the modified image processing as non-inferior will be calculated. Non-inferiority will be defined as a score of equivalence between modified and original or a score indicating the modified image processing is superior. For each reader, the proportion of cases judged as non-inferior with modified processing will be calculated for each feature and each view in Table 3. A pooled estimate will also be calculated where the results over all readers and views will be combined. 95% percentile bootstrap CIs will be constructed for the pooled proportions of cases judged as non-inferior with the modified processing. These CIs will be reported for each feature.

The null hypothesis is that the pooled proportion of cases judged as non-inferior with modified image processing is  $\leq$ 0.50, versus the alternative hypothesis that the pooled proportion is >0.50. If the 95% CI does not contain values  $\leq$ 0.50, then the null hypothesis will be rejected. These hypotheses will be evaluated for each of the seven general mammographic features. If the null hypothesis is rejected for each of the seven general features, then it will be concluded that the readers' subjective evaluation of the features on the modified imaging is non-inferior to the original imaging.

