### Acquisition of FFDM and DBT Images by ASPIRE Cristalle DBT Option (Figure A)

All FFDM and DBT images of the enrolled study subjects were acquired on the ASPIRE Cristalle system with DBT option. For each study subject, the DBT and FFDM images were acquired under the same breast compression for each of the LCC, RCC, LMLO and RMLO views.

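### Is one of the seven co-primary features left undefined because the synopsis calls it composition and Table 3 calls it compression?

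*Protocol*

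**What the plan says.** The protocol lists the graded features twice. In the synopsis, under Feature Comparison Study Design, item 2 begins "Breast composition, assessing overlapping breast structures, uniformity of exposure of fibroglandular tissues". In Section 8.4.1, Table 3, item 2 begins "Breast compression, assessing overlapping breast structures, uniformity of exposure of fibroglandular tissues, adequacy of penetration of thicker portions of the breast". Both lists number the features 1 to 11, and both state that items 8 to 11 will not be evaluated in this study. Items 1 to 7 are therefore the general features.

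Section 9 of the protocol ties the analysis to that table: the proportion of cases judged non-inferior "will be calculated for each feature and each view in Table 3". The Study Analysis part of the synopsis, Section 9.2 and SAP Section 1 describe the same calculation without naming the table. SAP Section 1 refers to seven general features and requires the null hypothesis to be rejected for every one of them, but it does not list them.

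Section 8.3 covers how readers learn the features: "Training will include review of the case report forms to ensure reader understanding of the mammographic features".

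**The concern.** Under an all-seven rule, a failure on any one feature defeats the claim, and a confidence interval is reported for each. A feature with two names raises the question of what was tested.

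The two words also have other uses in this protocol. Composition belongs to the BI-RADS density categories in the Definitions, for example "The breasts are heterogeneously dense, which may obscure small masses". Density is also a sampling target in Section 7.3.3, where "cases will be randomly selected so that approximately 10% have extremely dense breasts". Compression describes the state of the breast at acquisition. The definition of DBT images says projections are taken "over a limited angular range while the breast remains compressed and unmoved", and Appendix A says "the DBT and FFDM images were acquired under the same breast compression".

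The SAP is dated two months after the protocol (July 16 against May 15, 2018) and could have settled the name, but did not. If the two headings led readers to grade different things, one of the seven primary results would lack a fixed meaning. A user of the report might also take that line as a statement about density or about acquisition technique.

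**Working it through.** **1. What is graded under each heading.** In both lists the heading is followed by an instruction to assess named items.

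| Item assessed | Synopsis, *composition* | Table 3, *compression* |
|---|---|---|
| Overlap of breast structures | yes | yes |
| Evenness of exposure of fibroglandular tissue | yes | yes |
| Penetration of thick parts | yes | yes |
| Exposure of thin parts | yes | yes |
| Motion unsharpness | yes | yes |

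All five items agree, in the same order. The only other difference is a comma before the last item. Neither list adds density category or applied compression as something to grade.

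**2. What form the grade takes.** For every feature the reader compares the left and right images on a scale from -2 to +2. The two images show the same breast and differ in processing. The result is a proportion of cases scored as equivalent or better with modified processing. This is neither a density category from a to d nor a measure of compression.

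**3. Whether any planned figure depends on the heading.** The inputs come from protocol Section 9.3 and SAP Section 2: null proportion 0.50, multipliers 1.96 and 0.84, six readers and 600 cases. The plan's formula is

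M = {1.96 × √(0.5 × 0.5) + 0.84 × √(p(1 − p))}² / (p − 0.5)², with N = M/6.

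For p = 0.56:
- 1.96 × 0.5 = 0.980
- 0.84 × √(0.56 × 0.44) = 0.84 × 0.4964 = 0.417
- M = (1.397)² / 0.0036 = 542.09 with unrounded terms
- N = 542.09 / 6 = 90.35, rounded up to 91

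| p | M | M/6 | Rounded up | Plan |
|---|---|---|---|---|
| 0.55 | 781.64 | 130.27 | 131 | 131 |
| 0.56 | 542.09 | 90.35 | 91 | 91 |
| 0.57 | 397.64 | 66.27 | 67 | 67 |
| 0.60 | 193.63 | 32.27 | 33 | 33 |

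Power for a single feature with 600 cases at p = 0.56 is Φ[(√600 × 0.06 − 0.98) / 0.4964] = Φ(0.987) = 83.8%. The exact binomial test, which rejects at 325 or more of 600, gives 82.8%. Both agree with the plan's statement of slightly more than 80%. The name of a feature enters none of these expressions, so the figures are the same under either heading.

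**4. Whether the SAP leaves the set of seven open.** The SAP title names protocol FMSU2017-003. Section 9 of that protocol points to Table 3, and Section 8.4.1 numbers the items and sets 8 to 11 aside. An analyst who follows this path reaches items 1 to 7 and no other set.

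The missing table reference does not show that the SAP removed a pointer. On this sentence the SAP wording matches the synopsis, which never had one. The SAP's concluding sentence follows Section 9 instead, so which text was the source cannot be told.

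**The case for a change.** The strongest case for acting is that the text of a primary endpoint should use one word in every place. These are two complete English words with different meanings in this protocol, and a misread character does not explain the difference. The descriptors do not decide between them: overlap and motion unsharpness fit compression, while exposure of fibroglandular tissue fits composition. The SAP leads back to two headings without saying which governs. A reader who graded by the heading alone might also see no difference between two images of the same breast and score 0, which counts as non-inferior.

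The mismatch stands, and so does the point that the SAP does not resolve it. The consequences are weaker:

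- **Scoring 0 by the heading.** This risk is the same under either word, because neither density category nor applied compression should differ between two reconstructions of one breast. Settling on one word would not remove it. The descriptors, the training on the form and the instruction to use 0 sparingly bear on it, and all three are already in the plan.
- **Misreading of the report.** This supposes that a line in a table of left-against-right preference proportions would be taken as a density or acquisition result. The documents contain no table layout that would show this.
- **A conflict in what readers saw.** This cannot be shown, because the case report form is not available.

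**Conclusion.** This is a clerical slip in the heading of one feature out of seven. The graded content of feature 2 is fixed by five descriptors that agree in both places, and the seven features can be identified from the protocol to which the SAP belongs. No grade, hypothesis, confidence interval, sample-size entry or power figure changes under either name. The absence of a feature list in the SAP is missing detail that an analyst fills from Table 3, not a contradiction.

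The conclusion rests on two assumptions: that the case report form carries the same five descriptors as the protocol, and that readers grade by them as trained. If the form showed only the bare heading, the choice of word would matter more, but nothing in the documents suggests that it does. Using one word throughout would be ordinary copy-editing and would alter no result, so no change to the plan is called for.
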